9.5 Population Sets

For analyses on the Safety Analysis Sets (SAS, SAS 2, and SAS for Solicited Adverse Events [SASsol]), subjects are analyzed in the group of treatment they actually received (“as treated”). Based on the number of subjects receiving treatment not as randomized, selected efficacy analyses performed on the SAS “as treated” may be repeated on the SAS, analyzing subjects under the treatment they had actually been randomized to.

If a subject received both the active vaccine and the placebo (i.e. at the two different vaccinations), subjects are analyzed in the active vaccine group for “as treated” analyses.

Following the intent-to-treat principle, in the Efficacy Sets and Per-Protocol Sets, subjects are analyzed in the group to which they were randomized (“as randomized”).

Any analyses using all randomized subjects are based on vaccination “as randomized”.

9.5.1 Safety Analysis Set

The SAS includes all subjects randomized in the trial who received at least one dose of any lot of CVnCoV or placebo vaccine.

9.5.2 Immunogenicity/Reactogenicity Subset

The Immunogenicity/Reactogenicity Subset is defined as all subjects from the immunogenicity/reactogenicity cohort as indicated on the CRF (i.e. the first 1260 subjects enrolled into the study).

9.5.3 Safety Analysis Subsets (SAS 2 and SASsol)

- The SAS 2 includes all subjects of the SAS who belong to the Immunogenicity/Reactogenicity cohort.
- The SASsol includes all subjects of the SAS who belong to the Immunogenicity/Reactogenicity cohort with at least 1 diary collection indicating the occurrence or lack of occurrence of solicited AEs (see Section 10.5.2).

9.5.4 Per Protocol Immunogenicity (PPI) Set

The PPI set includes 250 subjects (100 per lot and 50 placebo subjects) from the Immunogenicity/Reactogenicity Subset who:

- Received both doses as randomized and within the windows defined in the protocol.
- Have no major protocol deviations expected to impact the immunogenicity outcomes as specified in Section 12.5.
- Have not received medical treatments (such as blood products, immunoglobulin therapy) that may interfere with one or both of the proposed immunogenicity measurements.
- Have at least one blood sample collected at baseline and at 14 days (Day 43) post-second vaccination available for analysis.

Subjects who have been tested positive for COVID-19 have their data included up to the point of a positive test result.

Subjects to be excluded from the PPI set are identified and reviewed at the Blinded Data Review Meeting held before any formal analysis (interim or final). See Section 12.5 for further details.

The selection of the 250 applicable subjects is performed by the Sponsor and communicated at the Blinded Data Review Meeting performed before the EOT analysis.

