- k. Binding antibodies to the RBD (receptor-binding domain) of the S (spike) protein and to the N (nucleocapsid) protein of SARS-CoV-2 will be measured by immunoassay. Viral neutralizing antibodies directed against SARS-CoV-2 will be measured by a functional activity assay. The N protein is not a component of the CVnCoV vaccine, but is being measured to determine serostatus of subjects to the SARS-CoV-2 virus (naïve or non-naïve to SARS-CoV-2); distinguish immune responses elicited by infection with SARS-CoV-2 from those induced by CVnCoV vaccination; and determine the occurrence of SARS-CoV-2 infection during the trial.
- l. Blood will be collected for measurement of antibody responses on Days 1, 29, 43, 57, 120 and 211, and cell-mediated immunity on Days 1, 29, 43, 57, 120, and 211 for a total volume of up to 318 mL.

**Table 2 Schedule of Trial Assessments and Procedures for All Other Subjects and for Subjects who, Following Unblinding, Receive an Authorized Vaccine After Having Received at least One Dose of CVnCoV**

(n=1,260)

	Vaccination Period				Follow-up Period			End of Trial
	Clinic Visit			Phone Call	Phone Call	Clinic Visit	Phone Call ii	Clinic Visit
Clinic Visit Number	1 a	2	3	-	-	4	-	5
Visit Window (days)	n/a	-3/+7	-3/+3	-3/+7	-7/+7	-7/+7	-7/+7	-0/+21
Trial Day	1	29	43	57	120	211	302	393
Vaccination Day (Reference for post-vaccination time points)	-	1	29+14	29+28	29+91	29+182	29+273	29+364
Visit Week (Wk) / Month (M)		Wk 4	Wk 6	Wk 8	M 4	M 7	M 10	M 13
Signed informed consent	X							
Inclusion/exclusion criteria	X							
Demographics	X							
Medical history	X							
Medication/vaccination history b	X							
Urine pregnancy test c	X	X						
Trial Vaccination								
Review criteria for delay or cancellation of trial vaccination d	X	X						
Administration of CVnCoV or control vaccine (observer-blinded)	X	X						
Safety Monitoring								
Physical examination e	X							X
Symptom-directed physical examination e		X	X			X		
Vital signs e,f	X f	X f	X			X		X
Collection of following AEs through the eDiary g :								
• Medically-attended AEs	X	X	X	X	X	X		

	Vaccination Period				Follow-up Period			End of Trial
	Clinic Visit			Phone Call	Phone Call	Clinic Visit	Phone Call i	Clinic Visit
Clinic Visit Number	1 a	2	3	-	-	4	-	5

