10.6.1 SARS-CoV-2 Serology Status

In all trial subjects, measurement of binding antibodies to the SARS-CoV-2 N protein is performed by immunoassay. Blood samples are taken on Day 1 (pre-vaccination baseline), Day 43 and Day 211 of the trial.

The (retrospective) SARS-CoV-2 serology status is defined based on levels of antibodies to the SARS-CoV-2 N protein. Subjects are defined as naïve to SARS-CoV-2 infection at baseline and Day 43, if there are no detectable SARS-CoV-2 N protein antibodies in the blood samples taken at baseline and Day 43, respectively.

Serology status at baseline is based on blood samples taken at Clinic Visit 1 (Visit Day 1) up to 2 days after 1st vaccination. The baseline definition for serology status is differing from the general baseline definition in this study (see Section 10.1).

Serology status at Visit Day 43 is based on blood samples taken at Clinic Visit 3 (Visit Day 43) 14 days after 2nd vaccination +/- 3 days.

For safety analyses, N antibody serostatus at baseline is used to define the seronegative and seropositive safety populations.

For the efficacy analyses, the subject must be seronegative/naïve to N protein at baseline and Day 43 to be considered naïve when COVID-19 cases are being counted ≥ 15 days after second trial vaccination. For endpoints where cases are counted at any time after the 1st trial vaccination, these subjects only have to be seronegative/naïve at baseline.

The same definition as given above is applied to assess the SARS-CoV-2 serology status of subjects at any other timepoint where a respective blood sample was taken; to measure infections with SARS-CoV-2 during the course of the trial.

Nota bene: Although the N antibody serostatus is to be considered an immunogenicity assessment, these values are not censored due to AV receipt.

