10.6.2.1 SARS-CoV-2 RBD of S Protein Antibodies

In subjects who tested seronegative to the N protein for SARS-CoV-2 at baseline (see Section 10.6.1), seroconversion is defined as a fold increase above 1 in antibody titer against SARS-CoV-2 RBD of S protein.

In subjects who tested seropositive to the N protein for SARS-CoV-2 at baseline (see Section 10.6.1), the definition for seroconversion is a fold increase above 2 in antibody titer against SARS-CoV-2 RBD of S protein versus baseline.

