10.8 Definition of Asymptomatic Cases of SARS-CoV-2 Infection and Onset Date

There is no active surveillance in this trial for asymptomatic SARS-CoV-2 infections. Subjects are reminded to contact the trial site immediately if he/she had a positive SARS-CoV-2 test performed outside of the trial site, whether or not they were symptomatic (COVID-19 illness) or asymptomatic at the time of the test.

If the subject was asymptomatic, trial staff contacts the subject immediately to collect information about the positive SARS-CoV-2 test the subject reported. The subject should be retested as soon as feasible to confirm the result. A positive RT-PCR test result is considered definitive as a virologically-confirmed case of SARS-CoV-2 infection.

If the subject is confirmed to have SARS-CoV-2 infection, the subject is followed by trial staff for at least 2 weeks for the development of any COVID-19 symptoms, to ensure that this is an asymptomatic infection. If the subject develops COVID-19, he/she is followed up as a COVID-19 case. If the subject is confirmed to be an asymptomatic infection, information is collected by the trial staff and documented on the appropriate CRF page.

The onset date of an asymptomatic infection is defined as the date of the positive RT-PCR test result performed by a central laboratory.

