12.7 Immunogenicity Analyses

For subjects in the Immunogenicity/Reactogenicity Subset, blood samples for SARS-CoV-2 viral neutralizing activity and antibody to SARS-CoV-2 RBD of S protein testing are collected on Day 1, Day 29 and Day 43.

In general, all analyses of SARS-CoV-2 RBD to S protein antibodies and SARS-CoV-2 viral neutralizing antibody levels are performed based on the PPI, for the pooled CVnCoV lots, split by lot and for placebo, and separately in subjects seronegative to the N protein at baseline and in subjects seropositive to the N protein at baseline (see Section 10.6.1). Summary statistics presented include the Geometric Mean (GM) with corresponding geometric SD and 95% CI, as well as the Median, Min, Max, Q1 and Q3.

Total columns (or respective sections in graphs) are not provided for immunogenicity outputs.

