12.7.1 Primary Immunogenicity Analyses

SARS-CoV-2 RBD of S protein antibodies (expressed as GMT) are summarized descriptively. Summaries are provided at baseline and each post-baseline sampling timepoint. The fold change (FC) from baseline is further computed and summarized for Day 29 and Day 43.

For each post-baseline timepoint, the number and percentage of subjects seroconverting with any fold increase, a 2-fold increase and a 4-fold increase are presented together with the exact 95% Pearson-Clopper CIs for the proportion of seroconverting subjects. This analysis is only done for subjects seronegative to the N protein at baseline. For a definition of seroconversion for subjects seronegative at baseline, see Section 10.6.2.

GMTs of SARS-CoV-2 RBD of S protein antibody levels over time are presented in the following figures:

- Line plot of GM FC from baseline and 95% CIs,
- Line plot of GMTs with GM and 95% CIs,
- Boxplots of GMTs with median, Q1 and Q3, and whiskers representing minimum and maximum by vaccine group.

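### The primary immunogenicity tables cut off titres after a positive COVID-19 test, but no visible rule uses N-protein seroconversion at Day 43

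*SAP*

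**What the plan says.** SAP 9.5.4 begins "The PPI set includes 250 subjects (100 per lot and 50 placebo subjects) from the Immunogenicity/Reactogenicity Subset who" and gives four criteria: doses as randomized and in window, no major deviation affecting immunogenicity, no interfering treatment, and samples at baseline and Day 43. It adds one rule on infection: "Subjects who have been tested positive for COVID-19 have their data included up to the point of a positive test result". Protocol 10.2.3 has neither that rule nor any criterion on N serology.

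SAP 12.7 presents the RBD and neutralizing titres "separately in subjects seronegative to the N protein at baseline and in subjects seropositive to the N protein at baseline". For seroconversion, SAP 12.7.1 states: "This analysis is only done for subjects seronegative to the N protein at baseline". The RBD threshold is low: in these subjects, under SAP 10.6.2.1, "seroconversion is defined as a fold increase above 1 in antibody titer against SARS-CoV-2 RBD of S protein". SAP 10.6.2.2 applies the same threshold to neutralizing antibodies.

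The N antibody is scheduled in all subjects. SAP 10.6.1 states: "Blood samples are taken on Day 1 (pre-vaccination baseline), Day 43 and Day 211 of the trial". Footnote k to protocol Table 1 gives as one reason for measuring it to "distinguish immune responses elicited by infection with SARS-CoV-2 from those induced by CVnCoV vaccination". SAP 9.5.5 requires N-negativity at baseline and at Day 43 for the Efficacy Analysis Set (EAS). SAP 12.2 tabulates Day 43 N status as a subject characteristic, but no titre analysis uses it.

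On detection, SAP 10.8 says: "There is no active surveillance in this trial for asymptomatic SARS-CoV-2 infections". RT-PCR testing follows reported symptoms or a positive test outside the site.

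**The concern.** By cutting titres off at a positive test, the plan accepts that antibody measured after an infection does not describe the response to the trial injections. The cut-off works only for infections that lead to a test. An infection without symptoms and without an outside test leaves no positive result, but it can leave N antibody at Day 43, because N is not in the vaccine. The plan uses that marker to define naive subjects for efficacy and not for immunogenicity.

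A Day 43 N-converter would therefore stay in the baseline-seronegative GMT, fold-change and seroconversion tables, with RBD and neutralizing values that may come partly or wholly from infection. In the placebo group this would appear as a response to saline. In the CVnCoV groups it would raise the GMT. The tables concerned report the primary immunogenicity endpoint and the secondary neutralizing endpoint.

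**Working it through.** The documents give no power, effect size or SD for the immunogenicity objective. The 250 is a count without a derivation, so there is no stated figure to reproduce. The check has a textual part and an illustration of size.

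**Text**

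| Analysis | N status used | Source |
|---|---|---|
| EAS and efficacy case definition | Baseline and Day 43 | SAP 9.5.5, 10.7.4 |
| RBD and neutralizing GMT, fold change | Baseline | SAP 12.7, 12.7.1, 12.7.2 |
| Seroconversion | Baseline | SAP 12.7.1, 12.7.2 |
| PPI membership | None stated | SAP 9.5.4, protocol 10.2.3 |

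SAP 9.5.4 does not define the positive test. SAP 10.7.2 defines a confirmed case by RT-PCR, and SAP 10.6.1 calls N results seropositive or seronegative. The natural reading is that an N result does not trigger the cut-off.

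**Size**

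Inputs from the documents: 50 placebo subjects, 100 per lot, values below LLOQ set to half LLOQ (SAP 10.3).

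Assumed, because the documents give neither: an undetected-infection rate q of 0.5% to 3% from Day 1 to Day 43, and a fold rise F in an infected subject's titre over what it would otherwise have been.

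1. Expected count = nq. Placebo: 50 × 0.005 = 0.25 to 50 × 0.03 = 1.5. Per lot: 100 × 0.005 = 0.5 to 100 × 0.03 = 3.

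2. Chance of at least one = 1 − (1 − q)^n. Placebo: 1 − 0.995^50 = 22% to 1 − 0.97^50 = 78%. Per lot: 1 − 0.995^100 = 39% to 1 − 0.97^100 = 95%.

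3. Placebo seroconversion, Clopper-Pearson two-sided 95% limits. For 0/50 the upper limit is 1 − 0.025^(1/50) = 7.1%. For 1/50 = 2% the interval is 0.05% to 10.6%.

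4. GMT factor with k infected of n = F^(k/n).
   - Placebo, k = 1: 20^(1/50) = 1.062 and 100^(1/50) = 1.096. Starting from half LLOQ, the placebo GMT goes to about 0.53 to 0.55 LLOQ.
   - Lot of 100: 5^(1/100) = 1.016 for one subject at F = 5, and 10^(3/100) = 1.072 for three at F = 10. At the expected count for q = 0.5%, 5^(0.5/100) = 1.008.

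5. Comparison with sampling error, assuming a log10 SD of 0.4 to 0.5 (not in the documents). The 95% interval of a lot GMT is a factor of 10^(1.984 × SD/√100), that is 1.20 to 1.26, either way.

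**The case against.** - **Unseen rules.** SAP 12.5 says the separate Appendix 5 covers deviations and other grounds for exclusion from the analysis sets, and the sponsor selects the 250 on criteria not shown. Either could already remove N-converters. This stands as a limit on certainty. A reader might infer that infected subjects definitely remain in the set; the documents show only that no visible rule removes them.
- **Meaning of N conversion.** A reader might take N-negative then N-positive as proof of infection within the six weeks. An infection just before Day 1 gives the same pattern, since there is no RT-PCR screening at enrollment. So does a false-positive result: N is qualitative, and no specificity or confirmation rule is stated. This stands, and is why results should also be shown without the exclusion.
- **Asymptomatic is not undetected.** Health care workers may be screened routinely, and outside positives are retested by RT-PCR (protocol 9.2.2). Once confirmed, they fall under the existing rule. The undetected rate is therefore below the total asymptomatic rate.
- **Small effect, no test.** Protocol 10.3.6 plans no formal hypothesis. SAP 6.1 item 12 drops lot-to-lot consistency, so a reader who infers a compromised lot comparison is mistaken; titres are only displayed by lot. The lot GMT shifts in step 4 lie well inside the sampling error in step 5, and the placebo GMT stays below quantification.
- **Protocol uses of N.** Protocol 9.4.2 lists two uses, neither of them PPI exclusion. Footnote k states why N is measured and does not set an analysis rule. The gap is thus an inconsistency of principle and breaks no explicit requirement.
- **Timing.** SAP 6.0 says version 4.0 was written by an unblinded team, and an immunogenicity delivery was scheduled for August 2021. A new exclusion comes after unblinding and must be declared so.

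**Conclusion.** The concern holds in a limited form. The visible text removes titres after a positive COVID-19 test but leaves a Day 43 N-converter in the baseline-seronegative RBD and neutralizing tables, unless Appendix 5 or the selection of the 250 removes that subject. Such a subject is probably, not certainly, an infection around or after Day 1.

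For the CVnCoV GMT the effect is a few percent per lot at most under the assumed rates and fold rises. It is clearest in placebo seroconversion, where a single subject accounts for the whole move from 0% to 2%, because any rise above 1-fold counts. The chances in step 2 depend entirely on assumed q and would be overstated if q were read as the total asymptomatic rate. No error rate, power or planned lot comparison is affected. This is a cheap improvement to a descriptive primary analysis.

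**What to change.** In SAP 9.5.4 and 12.7:

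1. Treat N-seropositivity at Day 43 in a baseline N-negative subject like a positive COVID-19 test. Exclude that subject's Day 43 RBD and neutralizing results from the baseline-seronegative GMT, fold-change and seroconversion tables.
2. Show the Day 43 tables without this exclusion as well, because N is unconfirmed and the rule would be added after unblinding.
3. Show Day 29 with and without these subjects, since N is not tested at that visit.
4. List the subjects by group, and record in the SAP change log and section 6.1 that the change was made after unblinding.
5. If Appendix 5 or the selection criteria already contain an N rule, state it in 9.5.4.

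The cost is SAP wording, a small number of extra tables and perhaps a few of the 250 subjects lost from some tables. N sampling is scheduled at the same Day 1 and Day 43 visits at which the PPI set requires samples; protocol 9.4.2 cancels only the Day 393 measurement. An infection shortly before Day 43 may not yet show N antibody, so the change reduces the contamination without removing it.

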9.5.5 Efficacy Analysis Set (EAS)

The EAS includes all subjects of the SAS who:

- Received both trial doses according to their randomization (two doses of the same lot of CVnCoV if randomized to that lot or two doses of placebo if randomized to placebo).
- Had not developed a virologically-confirmed case of COVID-19 before trial entry (based on exclusion criteria 1, see Trial Protocol)
- Had not developed a virologically-confirmed case of COVID-19 (definition in Section 10.7.2) or an asymptomatic case of SARS-CoV-2 (definition in Section 10.8) before 15 days after the second vaccination.
- Had not stopped the trial before 15 days after the second vaccination.
- Were SARS-CoV-2 naïve at baseline (Visit Day 1) and Visit Day 43 (based on seronegativity to N protein in the blood sample).
- Were not unblinded or in receipt of AV prior to 15 days after the second vaccination (See Section 10.10)

Where available the information assessed by the independent adjudication Committee of clinicians (Section 10.7.5) is used.

9.5.6 Efficacy Analysis Set for Seroconversion for N Protein Antibodies (EASS)

Not further applicable.

9.5.7 Summary of Analysis Sets to be Used per Analysis

Table 3 and

Table 4 provide an overview on the Analysis Sets used for the analyses of each endpoint.

Table 3: Summary of Analysis Sets to be Used per Analysis - Safety and Immunogenicity Endpoints

Endpoint Type	Endpoint Short Description	Analysis Set
Primary safety endpoint	Occurrence, intensity and relationship of medically-attended AEs	SAS
	Occurrence, intensity and relationship of SAEs and AESIs	SAS
	Occurrence of fatal SAEs	SAS
	Occurrence of AEs leading to vaccine withdrawal or trial discontinuation	SAS
	Occurrence, intensity and duration of solicited local AEs	SASsol
	Occurrence, intensity and duration of solicited systemic AEs	SASsol
	Occurrence, intensity and relationship of unsolicited AEs	SAS 2
Primary Immunogenicity Endpoint	Serum antibodies to SARS-CoV-2 RBD of S protein	PPI
	Seroconversion to SARS-CoV-2 S RBD protein	PPI#
Secondary Immunogenicity Endpoint	Serum neutralizing antibodies to SARS-CoV-2 virus	PPI
	Seroconversion to SARS-CoV-2 virus	PPI#
	Lot-to-Lot consistency of 2 CVnCoV lots, based on antibodies to the SARS-CoV-2 RBD of S protein	PPI#
# restricted to subjects naïve to SARS-CoV-2 N protein antibodies at baseline		

Table 4: Summary of Analysis Sets to be Used per Analysis - Efficacy Endpoints

Endpoint Type	Endpoint Short Description	Primary Analysis Set	Supportive Analysis Set
Secondary Efficacy Endpoint	First episodes of COVID-19 cases.	EAS	SAS#
	Severity assessment of first episodes of COVID-19 cases.	EAS	SAS#
	BoD Scores	EAS	SAS#
	Second episodes of COVID-19 cases	EAS	SAS
Exploratory Efficacy Endpoint	Second episodes of COVID-19 cases	EAS	SAS

#Including all subjects whatever their serological status at baseline and considering all events occurring at any time after the first trial vaccination.

10.0 Conventions and Derivations

10.1 Baseline and Change from Baseline

Unless otherwise stated, baseline is defined as the last non-missing measurement at Visit 1 (Day 1), prior to administration of the first dose of trial vaccine.

Change from baseline at any post baseline timepoint is defined as:

$$\text{Change from baseline} = \text{Observed Value at post baseline timepoint} - \text{Observed value at baseline.}$$

10.2 Trial Day

Throughout this trial, trial days are defined as follows:

- Day 1 is the day of first trial vaccination.
- For days after first trial vaccination, trial day is calculated as

$$\text{Trial Day} = \text{Date of day} - \text{Date of first vaccination} + 1.$$

- For days before first trial vaccination, trial day is calculated as

$$\text{Trial Day} = \text{Date of day} - \text{Date of first vaccination.}$$

10.3 Missing Data

In general, no imputation of missing values is done except for the following:

- Imputation of missing onset date for confirmed COVID-19 cases as specified in Section 10.7.2.
- For SARS-CoV-2 RBD of S protein antibodies, and viral neutralizing antibodies, concentration values marked as below the lower limit of quantification (LLOQ) are set to 0.5*LLOQ for computation purposes.
- Imputation of (partially) missing AE start dates:
 - If start date year value is missing, the date uncertainty is too high to impute a rational date. Therefore, if year value is missing, the imputed AE start date is set to missing.
 - If start date year value is before the vaccination start date year value, then the AE started before the vaccination. Therefore:
 - If month is missing, the imputed start date is set to the mid-year point (i.e., 01JULYYYY).
 - If month is not missing, the imputed start date is set to the mid-month point (i.e., 15MONYYYY).
 - If start date year value is equal to the vaccination start date year value, the start date month needs to be compared against the vaccination start date month, to determine the imputation rule to apply. Therefore:
 - If month is missing, the imputed month and imputed day is the same as start of vaccination
 - If month is lower than vaccination start date month and start date day is missing, the imputed start date is set to the mid-month point (i.e. 15MONYYYY).
 - If month is equal to the vaccination start date month and start date day is missing, the start day is set to the start day of vaccination.
 - If month is greater than the vaccination start date month and start date day is missing, the imputed start date is set to the beginning of the month (i.e., 01MONYYYY).
 - If start date year value is greater than the vaccination start date year value, the AE started after vaccination. Therefore:

- If month is missing, the imputed start date is set to the year start point (i.e., 01JANYYYY).
- If start date month is not missing and start date day is missing, the imputed start date is set to the beginning of the month (i.e., 01MONYYYY).
- If after imputation of start and resolution date (see below) a start date is after the resolution date (for example if a missing day of a start date is set to 15 and the resolution date is before the 15th of the same month and year) then the start date is set to the resolution date.
- Imputation of (partially) missing AE end dates:
 - If date of resolution is completely missing, and it is assumed that it resolved at the date of the end of the trial, the date of the end of the trial is used as the AE end date.
 - If year is present, it is assumed that it resolved on 31 December of that year (i.e., 31DECYYYY), or at the end of the trial if this is earlier and in the same year.
 - If year and month are present, it is assumed that it resolved on the last day of that month, or at the end of the trial if this is earlier and in the same month/year.
- Imputation of missing AE start times:
 - If the (recorded or imputed) AE start date is equal to the vaccination start date, then the AE start time is the time of vaccination start.
 - In all other cases, AE start time is imputed as 00:00.

If not stated otherwise, the original or incomplete data is presented in listings rather than the imputed one.

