10.5.4 Unsolicited AEs

Information on unsolicited AEs occurring on each vaccination day (i.e. dose 1 and 2) and the following 28 days after each dose is collected for subjects in the Immunogenicity/Reactogenicity subset. Data is recorded in the eDiary by the subject to aid AE reporting. The investigator reviews the eDiary and records information on any AEs on the CRF.

Unsolicited AEs are assigned to first or second dose based on the (reported or imputed) AE date. Unsolicited AEs occurring before dose 2 are assigned to dose 1. Unsolicited AEs occurring after dose 2, are assigned to dose 2. Unsolicited AEs occurring on the day of dose 2 are assigned to either dose 1 or dose 2 as per the following rules:

- If the AE occurred on the day of dose 2 but before vaccination with dose 2, the AE is assigned to dose 1
- If the AE occurred on the day of dose 2 but on or after vaccination with dose 2, it is assigned to dose 2.
- If the AE occurred on the day of dose 2 and it cannot be determined whether it occurred before, on or after vaccination with dose 2, it is assigned to dose 2.

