10.5.8 Overreported AEs

The definition of overreported AEs consists of the following 6 items:

No overreporting restrictions exist for:

1. (Treatment emergent) AESIs
2. (Treatment emergent) SAEs
3. (Treatment emergent) non-serious intercurrent medical condition that may affect the immune response to vaccination
4. (Treatment emergent) AEs leading to vaccine withdrawal or trial discontinuation

Overreporting restrictions:

5. Medically attended TEAEs not matching any of the above 4 categories that have started later than 6 months after 2nd dose
6. TEAEs not matching any of the above 5 categories that have started later than 28 days after any dose. (I.e. An AE starting between Day 29 and 49 when dose 2 was given on Day 50 is also an overreported AE.)

In the output, overreported AEs are displayed in listings but are not included in tables.

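### Partial AE start dates are imputed without looking at dose 2, so unsolicited AEs that began after dose 2 in its calendar month are credited to dose 1 or, when dose 2 is late, can drop out of the tables

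*SAP*

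**What the plan says.** SAP 10.3 gives the start-date rules. Each takes the vaccination start date as its reference, and dose 2 is not mentioned.

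- Day missing, AE in the month of dose 1: "If month is equal to the vaccination start date month and start date day is missing, the start day is set to the start day" on which vaccination began.
- Day missing, AE in a later month of the same year: "If month is greater than the vaccination start date month and start date day is missing, the imputed start date is set to the beginning", meaning the 1st.
- Day missing, AE in a later year: "If start date month is not missing and start date day is missing, the imputed start date is set to the beginning of the month".
- Month missing, same year as dose 1: "If month is missing, the imputed month and imputed day is the same as start of vaccination".
- Time missing: the vaccination time if the AE date is the vaccination start date. Otherwise, "In all other cases, AE start time is imputed as 00:00".

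The imputed date then drives the dose attribution. SAP 10.5.4 states: "Unsolicited AEs are assigned to first or second dose based on the (reported or imputed) AE date". Events before dose 2 go to dose 1. For an event on the day of dose 2, if "it cannot be determined whether it occurred before, on or after vaccination with dose 2, it is assigned to dose 2".

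SAP 10.5.8 defines overreported AEs, which are listed but not tabulated. They include "TEAEs not matching any of the above 5 categories that have started later than 28 days after any dose", and its worked example covers the interval between the end of the dose-1 window and a late dose 2. AESIs, SAEs, intercurrent conditions that may affect the immune response, and AEs leading to vaccine withdrawal or trial discontinuation carry no such restriction.

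**The concern.** Unsolicited AEs within 28 days after each trial vaccination are a primary safety endpoint (SAP 9.1.1) and are tabulated by vaccination (SAP 12.6.1.1). Several other AE classes are tabulated by vaccination as well (SAP 12.6.1.3). A rule that decides which dose an event belongs to therefore acts directly on a primary table.

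The rule treats the two doses differently. A day-missing AE in dose 1's month is placed on the dose-1 day. A day-missing AE in dose 2's month is placed on the 1st, which usually precedes dose 2. The 10.5.4 tie-break for ambiguous events points towards dose 2, while the 10.3 imputation points away from it. If partial dates are frequent, the dose-2 columns are understated and the dose-1 columns overstated.

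**Working it through.** The plan states no figure for this rule, so there is none to reproduce. The check applies the rules as written.

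**Inputs from the documents.** Dose 2 is scheduled for Day 29 with a window of −3/+7 days (Protocol Table 1 and 9.1.1.3). That is Day 26 to 36, or 25 to 35 days after dose 1. The unsolicited window is 28 days. The imputation and assignment rules are those listed above.

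**Assumptions not in the documents.** Dose 1 is uniform over every date in 2021, dose 2 is uniform over the window, and onset is uniform over the stated range after dose 2. Month and year are known and the day is missing.

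**Direction.** The imputed date is either the dose-1 day or the 1st of the AE month. Neither can fall after the true onset of an event that followed dose 1. An event that began before dose 2 is therefore never moved to dose 2, and all error runs from dose 2 to dose 1. The rule that sets a late start back to the resolution date only moves dates earlier.

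**Hand approximation.** An event is lost to dose 2 when its onset lies in dose 2's month and dose 2 is not on the 1st. With an average month of 365/12 = 30.42 days, the share is about 1 − (mean onset + 1)/30.42.

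- Onset 0–3 days: 1 − 2.5/30.42 = 91.8%
- Onset 0–7 days: 1 − 4.5/30.42 = 85.2%
- Onset 0–28 days: 1 − 15/30.42 = 50.7%

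**Full enumeration** (every dose-1 date, dose 2 at +25 to +35 days):

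| Onset after dose 2 | To dose 1 | Between windows | Not credited to dose 2 | Credited to dose 2 |
|---|---|---|---|---|
| 0–3 days | 85.5% | 6.3% | 91.8% | 8.2% |
| 0–7 days | 78.9% | 6.3% | 85.2% | 14.8% |
| 0–28 days | 44.7% | 6.0% | 50.7% | 49.3% |

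The fourth column is the sum of the second and third. For 0–28 days, dose 2 exactly on Day 29 gives 50.7% to dose 1 and 0% between windows. Dose 2 on Day 36 gives 32.5% and 18.2%. If Day 29 counts as outside the dose-1 window, as the 10.5.8 example implies, the between-windows share becomes 7.9% over the window and 20.9% at Day 36. Running dose 1 from mid-December 2020 to mid-June 2021 changes the 0–28-day results by at most 0.3 points.

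**Examples.**

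- Dose 1 on 10 January, dose 2 on 7 February, onset 12 February: imputed to 1 February, 22 days after dose 1, so dose 1.
- Dose 1 on 1 March, dose 2 on 5 April, onset 8 April: imputed to 1 April, 31 days after dose 1 and before dose 2, so out of the tables unless exempt.
- Dose 1 on 10 January, dose 2 on 7 February, onset 3 March: imputed to 1 March, correctly dose 2.

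**Effect of a dose-2 branch.** Suppose a missing day is set to the dose-2 date when month and year match dose 2 and differ from dose 1. Over the window, with no other data used:

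| Onset after the dose in question | Post-dose-2 AEs still lost to dose 2 | Post-dose-1 AEs moved to dose 2 (now 0%) |
|---|---|---|
| 0–3 days | 3.2% | 3.2% |
| 0–7 days | 1.7% | 8.7% |
| 0–28 days | 0.5% | 40.9% |

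For 0–28 days the last figure is 44.4% with dose 2 on Day 29, and 52.3% if the branch is also applied when both doses fall in one month.

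**The case against.** The strongest objection is that a dose-2 branch relocates the error. With uniform onset over 0–28 days and equal numbers of day-missing events after each dose, about half of 50.7%, or 25%, are misassigned now. After the change it is about (0.5% + 40.9%)/2 = 21%, so the gain is small. This stands for late-onset events. For onset within a week the gain is large, and information such as the AE end date or the record taken before the second injection can reduce the cost further.

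Second, the effect may be slight. Missing data are queried (Protocol 11.4), and diary entries are reviewed with subjects on Days 29, 43 and 57 (Protocol Table 1, footnote g). This also stands, because the number of partial dates is unknown.

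Four stronger readings are tempting, and the documents do not support them.

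- A reader might infer that the 00:00 rule certainly sends dose-2-day events to dose 1. SAP 10.5.4 assigns by date and sends undeterminable cases to dose 2, and imputed time is named only for treatment emergence (10.5.1). The two sections are unreconciled, and misassignment follows only if 00:00 is taken as determining the time.
- A reader might apply the 92% or 85% to all post-dose-2 AEs. They describe early onset with the day missing. Solicited AEs, which cluster there, are entered daily in a diary, go to dose 2 if they occur on its day (10.5.2), and are not analysed at end of trial (12.6.1.2).
- A reader might infer that every shifted non-serious AE leaves the tables. Most are credited to dose 1 and stay in the any-vaccination table. Removal requires dose 2 later than Day 29, and 10.5.8 exempts several categories. SAP 12.6.1.1 also plans a table of all reported AEs, including later ones, which conflicts with 10.5.8 and should be reconciled.
- A reader might infer bias against one arm. The rule is the same in all arms and safety is descriptive, so what is shown is misattribution between doses.

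**Conclusion.** The concern holds in a limited form. SAP 10.3 omits dose 2, and 10.5.4 and 10.5.8 act on the resulting date, so the error in a primary safety tabulation runs in one direction. About half of day-missing unsolicited AEs that truly followed dose 2 are not credited to it, and the fraction is higher for early onset. These shares rest on uniform dose dates, visit timing and onset. The 6% between windows depends on the spread of dose 2 over its window and is zero at Day 29. Month-missing AEs in the year of dose 1 all go to the dose-1 date. Year-missing AEs are linked to no dose (10.5.1). The shares apply only to partial dates, whose number the documents do not give. The change is worth making because it is cheap and follows the plan's own tie-break.

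**What to change.** 1. In SAP 10.3, add a branch. When the AE month and year are known, match those of dose 2 and differ from those of dose 1, impute a missing start day as the dose-2 date. Make an exception if the AE end date, or an AE record made before the second injection at the Day 29 visit, shows earlier onset. Keep the current rule when both doses fall in one month or the month is missing.
2. When the AE date is the dose-2 date and the time is missing, impute the dose-2 time, or state that the imputed 00:00 is not used for dose assignment.
3. Report the number of partial dates affected, with a sensitivity count under the current rule.

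The cost is a few SAP lines and minor reprogramming. Some day-missing AEs that began after dose 1 in dose 2's month will be counted to dose 2: about 3% to 9% for onset within 3 to 7 days, and 41% to 52% for uniform 0–28-day onset without other data. That is the direction 10.5.4 already takes. SAP 6.0 says that version 4.0 was written and approved by an unblinded team, so the change should be recorded as made after unblinding.
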